#### 3.3.6 Data collection

Data will be collected via a standardised CRF, with a full supporting SOP. The CRF will be completed by the clinical care team at the participating site that submitted the sample (during O1.1). The CRF will not contain any participant identifiable data; all data will be held against a pseudoanonymised study code, with the link back held by the clinical care team only. COMBACTE-CDI investigators will not access participant's notes or access the link back. Once the CRF data has been collected and validated and verified the link-back will be destroyed by the local study site.

Data will be collected on the following variables to examine risk factors for CDI;

- Prior treatment with cytotoxic drugs
- Prior treatment with PPIs
- Underlying diagnoses
- Co-morbidities
- Previous antibiotics (preceding 12 weeks)
- Previous hospitalisation (preceding 12 weeks)
- Admission history (if an in-patient)
- Residential status (if in the community), e.g. home/nursing home
- Previous CDI
- Kissing contact with an infant
- Known contact with CDI case
- Previous wards/movement within hospital

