#### 7.2 Univariate analysis

Univariate analysis will be used to assess outcomes and risk factors; continuous variables will be compared between cases and controls by t-test; categorical variables will be compared between cases and controls by chi-squared (fishers exact where numbers are below 5). Risk ratios (Odds ratio if it is case control study) will be calculated for CDI cases with identified variables of interest. Univariate analysis will be used to assess consistency between countries and between different healthcare settings.

The variables to be included in the univariate analysis are shown in the table in appendix 1.

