#### 7.3 Regression analysis (or Multivariate analysis)

To evaluate risk factors considering confounding, unconditional logistic regression analysis will be perform with case/control as dependent variable, and all variables listed in the univariate analysis as independent variables.

To build the logistic regression model, we will apply a stepwise forward selection to identity risk factors. The process of the forward selection will be recorded to rank the risk factor.

The regression analysis will be performed separately for the three age groups (18-49,50-64 and 65+ years). If there is a reasonable sample size analysis will also be performed for the age group <18 years.

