	CDI graded?			when the sample
				was taken
4.5.1	If yes, please record	Categorical	Univariate/multivariate	Patient admission
	the severity of CDI			when the sample
				was taken
4.6	Has the patient	Binary	Univariate	Patient admission
	ever had CDI			when the sample
E Clinica	Information			was taken
5.1	Temperature	Continuous	Univariate	Patient admission
5.1	(highest reading +/-	Continuous		when the sample
	3 days of the index			was taken
	sample)			
5.2	Serum creatinine	Continuous	Univariate	Patient admission
	(highest reading +/-			when the sample
	3 days of the index			was taken
	sample)			
5.3	White cell count	Continuous	Univariate	Patient admission

	(highest +/-3 days			when the sample
	of the index			was taken
	sample)			
5.4	Serum Albumin	Continuous	Univariate	Patient admission
	(lowest +/-3 days of			when the sample
	the index sample)			was taken
5.5	Primary diagnoses	Categorical	Univariate	Patient admission
	at time of index			when the sample
	sample			was taken
5.6	Does the patient	Binary	Univariate	Patient admission
	have any significant			when the sample
	illnesses			was taken
5.6.1	If yes, are the	Categorical	Univariate	Patient admission
	illnesses:			when the sample
				was taken
	Acute/chronic			
5.6.2	Please provide	Categorical	Univariate	Patient admission
	details of the			when the sample
	significant illness			was taken
5.7	Co-morbidities		All of these could be	
			Covariates	
	Myocardial	Binary	Univariate/multivariate	Patient admission
	infarction			when the sample
				was taken
	Congestive heart	Binary	Univariate/multivariate	Patient admission
	failure			when the sample
	De debe velo e e de c	D'		was taken
	Peripheral vascular	Binary	Univariate/multivariate	Patient admission
	uisease			when the sample
	Corobrovascular	Pipany	Univariato (multivariato	Rationt admission
	disease	Billary	Onivariate/multivariate	when the sample
	uiscase			was taken
	Dementia	Binary	Univariate/multivariate	Patient admission
	Dementia	Dinary		when the sample
				was taken
	COPD	Binary	Univariate/multivariate	Patient admission
		,	,	when the sample
				was taken
	Peptic Ulcer disease	Binary	Univariate/multivariate	Patient admission
				when the sample
				was taken
	Cystic fibrosis	Binary	Univariate/multivariate	Patient admission
				when the sample
				was taken
	Diabetes without	Binary	Univariate/multivariate	Patient admission
	organ damage			when the sample

			was taken
Leukaemia within	Binary	Univariate/multivariate	Patient admission

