	symptoms at time			was taken
	of index sample			
5.9	Was there an	Binary	Univariate	Patient admission
	alternative cause			when the sample
	for the patients			was taken
	diarrhoea			
5.9.1	If yes please give	Categorical	Univariate	Patient admission
	details			when the sample
				was taken
5.10	Duration of	Number of	Univariate	Patient admission
	diarrhoea before	days of		when the sample
	and after the index	diarrhoea is		was taken
F 44	sample	Continuous		Detionst e destade
5.11	Did the patient	віпагу	Univariate	Patient admission
	undergo any			when the sample
	diagnostic			was taken
	procedures for this			
	episode of CDI?			
5.11.1	It yes, please	Categorical	Univariate	Patient admission
	complete the table			when the sample

				was taken
5.12	Evidence of colitis	Binary	Univariate	Patient admission
				when the sample
				was taken
5.12.1	If yes please give	Categorical	Univariate	Patient admission
	details			when the sample
				was taken
5.13	Was the patient in	Binary	Univariate	Patient admission
	contact with a			when the sample
	diagnosed			was taken
	Clostridium difficile			
	case in the			
	preceding 3 months			
E 12 1		Catagorical	Univariato	Dationt admission
5.15.1	the date	Categorical	Univariate	when the sample
				was taken
5.14	Was the patient in	Binary	Univariate	Patient admission
	kissing contact of	Dinidi y	omratice	when the sample
	an infant in the			was taken
	preceding 3 months			
	to the sample?			
5.14.1	If yes please give	Categorical	Univariate	Patient admission
	the date			when the sample
				was taken
5.15	Did the patient	Binary	Univariate	Patient admission
	receive mechanical			when the sample
	ventilation			was taken
5.15.1	If yes, please give	Continuous	Univariate	Patient admission
	une duration of the			when the sample
	minutes			was taken
5.16	Was the patient	Binary	Univariate	Patient admission
	source isolated due			when the sample
	to CDI			was taken
5.16.1	If yes, please give	Continuous	Univariate	Patient admission
	the duration of			when the sample
	source isolation in			was taken
	days			
5.16.2	Did the patient in	Binary	Univariate	Patient admission
	source isolation			when the sample
	lead to the blocking			was taken
- 10 -	of beds			
5.16.3	If yes, how many	Continuous	Univariate	Patient admission
	beas were blocked			when the sample
6 Dave 11	uuring that time?			was taken
6. Drug H	istory			

6.1	Was the patient prescribed	Binary	Univariate/multivariate	Patient admission when the sample was taken

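### SAP 7.3 and the Appendix 1 tags disagree on whether previous CDI, contact with a CDI case and kissing contact with an infant can enter the adjusted risk-factor model

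*SAP*

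**What the plan says.** SAP 7.3 gives the purpose and content of the adjusted analysis: "To evaluate risk factors considering confounding, unconditional logistic regression analysis will be perform", with case/control status as the dependent variable and "all variables listed in the univariate analysis as independent variables". The model is then built by selection: "we will apply a stepwise forward selection to identity risk factors", and the order of entry is used to rank the factors. SAP 7.2 identifies the univariate list: "The variables to be included in the univariate analysis are shown in the table in appendix 1".

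Appendix 1 has an analysis-type column with two different entries, 'Univariate/multivariate' and 'Univariate'. Three items carry the second entry alone:

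- Item 4.6, whether the patient has ever had CDI: "4.6 Has the patient Binary Univariate Patient admission".
- Item 5.13, contact with a diagnosed case in the three months before: "5.13 Was the patient in Binary Univariate Patient admission".
- Item 5.14, the "kissing contact of" an infant item, also over three months, with the same tag.

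Protocol 3.3.6 lists 12 variables collected to examine risk factors. Previous CDI, kissing contact with an infant and "Known contact with CDI case" are three of them.

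**The concern.** The two parts of the SAP give different candidate sets for the same model, and no text ranks one above the other. An analyst could settle the matter after seeing the data.

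The choice affects planned exposures. Protocol 3.3.1 argues that earlier work centred on antibiotics and so had less chance of finding other modifiable factors. The two contact items are of that kind. Under the tags they would be reported only as crude comparisons, and they could not appear in the ranking that 7.3 takes from the selection order. Previous CDI is not modifiable, but it is a plausible confounder of antibiotic and healthcare exposure, and under the tags it would be unavailable for adjustment.

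**Working it through.** The main check is a comparison of texts. The plan gives no figure to reproduce.

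**1. The rule in the body of the SAP.** 7.2 makes Appendix 1 the univariate list, and 7.3 enters that whole list. On this reading 3 of the 3 items are regression candidates.

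**2. The rule in Appendix 1.** All three items are tagged 'Univariate' only. On this reading 0 of 3 are candidates, so 3 of the 12 protocol risk factors (25%) cannot get an adjusted odds ratio. Three is a minimum: the protocol's underlying diagnoses correspond at least in part to items 5.5 and 5.6 to 5.6.2, which are also 'Univariate' only, although the itemised co-morbidities in 5.7 are tagged for both.

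**3. Do the tags follow a timing or causal rule?** Set side by side, they do not:

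- Pre-sample and tagged for both: healthcare contact (2.6), antibiotics (6.2), PPIs (6.3), steroids and immunosuppressants (6.5), surgery (8.1).
- Pre-sample and 'Univariate' only: 4.6, 5.13, 5.14.
- Arising after the sample, or a consequence of CDI, and tagged for both: discharge destination (2.4), CDI-related purchases (2.9), escalation of CDI medication (7.1), death within 30 days (10.5), death between 30 days and 6 months (10.7).

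So the tags cannot be adopted as they stand to define a risk-factor model.

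**4. Time windows.** Items 4.6, 5.13 and 5.14 all carry the index admission as their window, while their wording refers to any time in the past (4.6) or the three months before (5.13, 5.14). Chemotherapy and radiotherapy in the preceding 12 weeks have the same entry, so it looks like a default.

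**5. Previous CDI and the selection of controls.** SAP 4.1.5 removes controls with a CDI-positive sample within 8 weeks before or after the index sample. No matching rule is stated for cases. Previous CDI is therefore lowered in controls partly by design. Item 4.6 is a yes/no item and cannot separate the last 8 weeks from earlier history. Item 4.1.1 records dates and results of CDI tests in the six months before the sample.

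**6. Illustration of leaving previous CDI out.** All inputs here are assumptions; none comes from the documents. Take an exposure with no effect of its own, present in a proportion e of patients with previous CDI and in 0.40 of the others. If previous CDI is present in a proportion p of a group, exposure in that group is P = p·e + (1 − p)·0.40. The crude odds ratio is [P_case/(1 − P_case)] / [P_control/(1 − P_control)]. Take p = 0.03 in controls.

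- Low end, p = 0.10 in cases, e = 0.60: P_case = 0.060 + 0.360 = 0.420; P_control = 0.018 + 0.388 = 0.406; OR = (0.420/0.580)/(0.406/0.594) = 1.06.
- High end, p = 0.25 in cases, e = 0.80: P_case = 0.200 + 0.300 = 0.500; P_control = 0.024 + 0.388 = 0.412; OR = (0.500/0.500)/(0.412/0.588) = 1.43.

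The high end implies an odds ratio for previous CDI itself of (0.25/0.75)/(0.03/0.97) = 10.8, which is large. The illustration says nothing about items 5.13 and 5.14.

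**The case against.** The strongest reply is that 7.2 and 7.3, read as written, already make all three items candidates, and that body text would ordinarily govern an appendix table. A reader might infer that these three factors will certainly get no adjusted odds ratio. The documents do not support that: it follows only if the tags override 7.3. This part of the reply stands. It does not remove the point, because a column that separates two analysis types has no function if every item enters the regression, and no text resolves the conflict.

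Further replies also stand:

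- Protocol 3.3.7 promises odds ratios without calling them adjusted, so no protocol commitment is broken. The aim of adjustment comes from SAP 7.3.
- Forward selection guarantees no variable an adjusted estimate, however it is tagged. Retagging makes the three items eligible and no more.
- A reader might count their absence from SAP 6.2 as a further defect. That section calls its list partial and refers to Appendix 1, where all three appear.
- The time-window entries are a labelling matter. The look-back is in the item wording, so the data collected are not in doubt.
- Forcing previous CDI into every model is debatable, given the control-only exclusion in SAP 4.1.5.

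**Conclusion.** The point holds as an unreconciled specification. Under one reading of the SAP, three of the protocol's 12 risk factors have crude estimates only and previous CDI is not available for adjustment; under the other, all three are candidates for selection. The documents do not say which applies and give no reason for treating these items differently from most comparable pre-sample exposures.

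The practical effect on other odds ratios cannot be sized from the documents. A reader might take 1.06 to 1.43 as an estimate of the bias. It is an illustration under assumed inputs only, negligible at one end and dependent on a very strong case-control difference in previous CDI at the other.

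The correction is worth making because it is cheap and prevents crude-only reporting of planned risk factors.

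**What to change.** In the SAP:

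1. Retag items 4.6, 5.13 and 5.14 'Univariate/multivariate' in Appendix 1. If any is left out on purpose, for example because the data are sparse, give the reason.
2. Correct their time-window entries to match the items: any time before the sample for 4.6, and the three months before the sample for 5.13 and 5.14.
3. State in 7.3 that the candidates for the risk-factor model are a named list of pre-sample exposures, including these three. Do not state that the existing tags define the model, since that would confirm discharge destination, purchases, treatment escalation and death as predictors of case status.
4. For previous CDI, either define it over a look-back that applies equally to cases and controls, or state that the estimate will be interpreted in the light of the 8-week exclusion of controls in 4.1.5.

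The cost is three tags, three window entries, a short list in 7.3 and one sentence on previous CDI. No new data are needed.

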## 2.1 Selection of case and controls (total possible to be recruited)

		Location	of participant a sample	at time of
Diagnostic categories:		Hospital	Community	TOTAL
CDI positive cases	1. CCNA positive	83	20	103
	2. CCNA negative/Simoa positive	49	22	71
	3. CCNA and Simoa negative but CTC positive or bioFire pos	24	15	39
CDI negative controls	4. Negative control *	365	147	512
Total number selected for case/control study 521 204		725		

Table1. The total number of samples selected for the case/control study (n=725). The table shows the number of CDI positive cases according to the indicated diagnostic categories (1-3, n=213) and by location of participant (Hospital n=156, Community n=57). Negative controls (4, n=512) were selected at a rate of 1:3 from matching participating sites (one case to three controls). As some participating sites had less than 3 controls per case, average rate was of 1:2.4 (one case to 2.4 controls) (\*).

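### SAP 7.3 ranks risk factors by their order of entry in an unrestricted forward search; entry order does not measure strength, and the search has no stated entry rule or protection against false factors

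*SAP*

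**What the plan says.** SAP 7.3 fits an unconditional logistic model with case or control status as the dependent variable and "all variables listed in the univariate analysis as independent variables". SAP 7.2 points to the source of that list: "The variables to be included in the univariate analysis are shown in the table in appendix 1". SAP 7.3 continues: "To build the logistic regression model, we will apply a stepwise forward selection to identity risk factors", and then: "The process of the forward selection will be recorded to rank the risk factor". The model is also split by age: "The regression analysis will be performed separately for the three age groups (18-49,50-64 and 65+ years", with under-18s added if numbers allow.

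The data available are in SAP 2.1, Table 1: "CDI positive cases according to the indicated diagnostic categories (1-3, n=213"), made up of 103, 71 and 39 in the three diagnostic classes, and 512 controls.

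The SAP gives no entry or stopping threshold, no cap on candidates, and no shrinkage, resampling or validation. The 5% error rate in SAP 3 belongs to single two-proportion comparisons and is not offered as an entry rule. SAP 7.2 promises odds ratios; neither 7.2 nor 7.3 mentions confidence intervals.

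**The concern.** The risk-factor aim is one of two main analysis objectives (SAP 2.5), and 7.3 is the only place where confounding is addressed. Two things go wrong if the rule is followed as written.

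First, forward selection adds at each step the candidate with the most significant conditional test. That test depends on effect size, exposure prevalence, the number of patients and what is already in the model. A list in entry order will be read as a list by importance, and it is not one.

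Second, a search over so many candidates with no stated threshold will admit null factors. Factors that are kept because they looked significant have estimates biased away from 1. Published odds ratios would then be too large, some named risk factors would be false, and the ranking would not be expected to replicate.

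**Working it through.** **1. The plan's own counts.** 103 + 71 + 39 = 213 cases; 365 + 147 = 512 controls; 213 + 512 = 725; 512/213 = 2.40. These reproduce Table 1.

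**2. Candidates (hand count of Appendix 1, before dummy coding).**
- Items marked for multivariate analysis: 86, or 74 without the section 10 outcomes.
- All univariate items: 120.
- Counting sub-rows: 113 marked multivariate, 149 in all.

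The range exists because SAP 7.3 admits every univariate variable, while the Analysis type column marks many items as univariate only. Cases per candidate are 213/149 = 1.4 to 213/74 = 2.9. The multivariate-marked items include consequences of CDI, such as graded severity (4.5.1), escalation of CDI medication (7.1) and CDI-linked death (10.5.1). These could enter early and be ranked as risk factors.

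**3. Ranking.** At the first step the score test for a binary exposure is

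z = (p1 − p0) / √[p̄(1 − p̄)(1/213 + 1/512)], with p1 = OR·p0 / (1 − p0 + OR·p0) and p̄ the pooled prevalence.

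- OR 3, p0 = 0.05: p1 = 0.15/1.10 = 0.136; p̄ = 0.0754; standard error 0.0215; z = 4.01.
- OR 2, p0 = 0.45: p1 = 0.90/1.45 = 0.621; p̄ = 0.500; standard error 0.0408; z = 4.19.

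Treating the two statistics as independent with unit variance, the stronger factor enters first with probability Φ[(4.012 − 4.187)/√2] = Φ(−0.12) = 0.45. Repeated simulations gave 44% to 46%. In a separate simulation with six true factors, one with odds ratio 3.5 and 5% prevalence was the strongest but entered first in 7% of runs. Its median position was third, behind commoner factors with odds ratios 2.5 to 2.9.

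**4. False entries.** With m null candidates and entry level α, about mα enter. For 95 nulls beside five true factors: 95 × 0.05 = 4.75 and 95 × 0.01 = 0.95. Simulated forward selection (100 independent binary candidates, five true odds ratios of 1.5 to 2, 213 v 512) gave 5.1 to 5.6 null factors at 0.05, with about 4 of the 5 true ones, and 1.2 null factors at 0.01. With no true factor among 100, the chance of at least one entry at 0.05 is 1 − 0.95^100 = 99%. An AIC-like entry level of 0.157 then admits 17 null factors on average.

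Null share of the selected variables, 100 candidates, with 3 to 12 true factors in the pooled rows:

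| Data | Entry level | Null share |
|---|---|---|
| Pooled, 213 v 512 | 0.05 | 36–63% |
| Pooled, 213 v 512 | 0.157 | 59–85% |
| Assumed 65+ stratum, 138 v 200 | 0.05 | 46–69% |
| Assumed small stratum, 35 v 140 | 0.05 | 77–87% |

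The 138 v 200 stratum applies the SAP 3 percentages: 0.65 × 213 = 138 and 0.39 × 512 = 200. With six true factors at 0.05, the pooled null share is 40% for 74 candidates and 61% for 149.

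**5. Estimates after selection (entry 0.05).**
- Pooled: odds ratios of selected true factors are inflated about 1.1-fold, and their nominal 95% intervals cover the truth 93–94% of the time. Selected null factors have a median odds ratio of about 1.6 to 1.7, and their intervals cover 1 in only 1–2% of cases. The reported standard error is 1.03 times that of the true model, so interval width is about right.
- Assumed age stratum of one third (213/3 = 71 cases, 512/3 = 171 controls): about 6 null and 2 of 5 true factors enter, with true odds ratios inflated about 1.6 to 1.7-fold.
- Smallest diagnostic class, 39 v 512, if the model is run by class as SAP 2.5 implies: 5.5 null and 1.7 true factors enter, with inflation about 1.7-fold.

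**The case against.** The strongest reply has four parts.

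- **The SAP never says that rank means strength.** With the three factors it powers on (age over 65, antibiotics, surgery; odds ratios 2.9, 2.5 and 1.8 from SAP 3), the strongest entered first in 78% of runs. That is true, but it holds because strength and significance happen to line up for those exposures. A ranking whose meaning is undefined and which fails for rare, strong exposures is still unsound.
- **A reader might infer that the search selects mostly noise.** The documents do not support that as a general statement. It depends on the unstated threshold and on the unknown number of true factors. In the pooled data at 0.05 the null share runs from about one third to two thirds, and at 0.01 only about one null factor enters. It becomes most of the selection under looser rules or in small strata.
- **A reader might also infer that the confidence intervals would be far too narrow.** They would not be: widths are close to correct, and the fault is bias from selection. At an entry level of 0.05, a null factor's interval excludes 1 almost by construction, so low overall coverage mainly restates the false-entry count. The SAP also promises no intervals.
- **An open search suits the aim.** Protocol 3.3.1 wants factors not yet recognised, and a short fixed list alone would work against that. This stands, and is why the search should be kept as exploratory.

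**Conclusion.** The ranking rule is wrong as written, whatever threshold is chosen: entry order follows conditional significance, and a clearly stronger but rarer factor can lose to a weaker common one more often than not (about 45% v 55% in the example). On the rest, the fault is an uncontrolled search. There is no entry rule or internal validation, with 1.4 to 2.9 cases per candidate. Under the stated assumptions, about 5 to 6 null factors enter at 0.05 and about 1 at 0.01. Bias in true factors is mild in the pooled data and about 1.5-fold or more in an assumed stratum of 71 v 171.

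These sizes assume independent binary candidates, chosen prevalences and true effects, and entry levels that the SAP does not state. The SAP gives no age distribution for this cohort, so the stratum figures are illustrations and not predictions. The point should be acted on before analysis, though it does not affect the data collected.

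**What to change.** 1. Delete ranking by order of entry from SAP 7.3.
2. Make the main risk-factor analysis one model with a short, pre-stated list of pre-index exposures, drawn from Protocol 3.3.6 and SAP 3 and 6.2: for example age, sex, setting, prior antibiotics, PPI use, prior hospitalisation, surgery and the comorbidity index. Report adjusted odds ratios with 95% confidence intervals. Ten terms would give 213/10 = 21 cases per term; the smallest class (39/10 = 3.9) would remain thin.
3. Before adding previous CDI, reconcile it with its univariate-only marking (Appendix 1, item 4.6) and with the removal of controls who had a CDI-positive sample within 8 weeks (SAP 4.1.5), which distorts that comparison.
4. Keep the wider search as a labelled exploratory analysis with a stated entry rule, bootstrap inclusion frequencies and shrunken odds ratios. First reconcile SAP 7.3 with the Analysis type column of Appendix 1, so that the candidate list is fixed, and take post-index items out of the risk-factor search.

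The cost is SAP wording and modest extra programming, with no new data. The downside is that fewer factors appear in the main model.

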#### 3. Sample size

Based on a previous risk factor study using a similar study design (ORCHID) the following power calculations were made;

Age >65; previously found 65% in cases and 39% in controls. Comparing proportions for equivalence, a sample size of 20 cases and 60 controls would give 80% power to detect a difference of 23% between cases and controls with an  $\alpha$  type one error rate of 5%.

At least one antibiotic; previously found 67% in cases and 45% in controls. Comparing proportions for equivalence, a sample size of 23 cases and 67 controls would give and 80% to detect a difference of 22% between cases and controls with an  $\alpha$  type one error rate of 5%.

At least one antibiotic; alternative single centre cohort found 85% in cases and 75% in controls. Comparing proportions for equivalence, a sample size of 92 cases and 276 controls would give and 80% to detect a difference of 13% between cases and controls with an  $\alpha$  type one error rate of 5%.

Previous surgery; previously found 26% in cases and 16% in controls. Comparing proportions for equivalence, a sample size of 156 cases and 469 controls would give and 80% to detect a difference of 10% between cases and controls with an  $\alpha$  type one error rate of 5%.

Previous surgery; alternative single centre cohort previously found 41% in cases and 28% in controls. Comparing proportions for equivalence, a sample size of 88 cases and 351controls would give and 80% to detect a difference of 13% between cases and controls with an  $\alpha$  type one error rate of 5%.

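### The adjusted risk-factor regression is planned only within age bands, so it gives no adjusted 65+ versus younger estimate and leaves the two younger bands sparse

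*SAP*

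**What the plan says.** SAP 7.3 describes an unconditional logistic regression, case versus control, to study risk factors with confounding taken into account. All univariate variables are candidates, chosen by forward selection, and the order of entry is used to rank them. It then states: "The regression analysis will be performed separately for the three age groups (18-49,50-64 and 65+ years". Under-18s get a model only if numbers allow. No model across all ages is named, and the age-band models are not described as additional to one.

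SAP 3 opens its power statements with age: "Age >65; previously found 65% in cases and 39% in controls".

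SAP 2.1 gives "the number of CDI positive cases according to the indicated diagnostic categories (1-3, n=213") and says "Negative controls (4, n=512) were selected at a rate of 1:3 from matching participating sites". It gives no age distribution.

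SAP 7.2 plans univariate comparisons of the Appendix 1 variables with no age restriction. Appendix 1 item 1.1 lists age as continuous, for univariate and multivariate analysis. SAP 4 says controls are initially matched on location only.

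**The concern.** Within a band that starts or ends at 65, a 65+ versus younger indicator does not vary, so no band model can estimate it. (The power section's cut is above 65 and the band is 65 and over. Patients aged exactly 65 do not restore the contrast.) Because controls are not matched on age, age is both a risk factor that could be estimated and a likely confounder. As written, the only adjusted analysis cannot report the first factor the SAP powers.

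The split also divides 213 cases among three models, each with its own forward selection from a long candidate list. Factors may enter in one band and not another by chance, and the entry order is to be read as a ranking. Without a planned test of age-by-factor differences, such lists could be mistaken for age-specific risk factors.

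**Working it through.** **1. Inputs.** From SAP 2.1: cases 103 + 71 + 39 = 213, controls 365 + 147 = 512, ratio 512/213 = 2.40, which agrees with the table. From SAP 3: age over 65 in 65% of cases and 39% of controls; control exposure 45% (any antibiotic) and 16% (previous surgery). Assumptions: these age proportions apply here, nobody is under 18, and younger patients split equally between the two lower bands. The odds ratio of 2 is also assumed. It lies between the values implied by SAP 3: (0.67/0.33)/(0.45/0.55) = 2.48 for antibiotics and (0.26/0.74)/(0.16/0.84) = 1.84 for surgery.

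**2. The plan's own figure.** SAP 3 says "a sample size of 20 cases and 60 controls would give 80% power to detect a difference of 23% between cases and controls". This does not reproduce. 65% versus 39% at 1:3 with 80% power needs 38 cases two-sided or 30 one-sided, and 20/60 gives 53% power two-sided. The stated 23% also differs from 65 − 39 = 26 points. That is a separate matter. What counts here is that the statement concerns a crude comparison of two proportions, for which all 213/512 give over 99% power.

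**3. Band sizes.**
- 65+: 213 × 0.65 = 138 cases; 512 × 0.39 = 200 controls.
- Each younger band: 213 × 0.35 / 2 = 37 cases; 512 × 0.61 / 2 = 156 controls.
- If 60% to 70% of cases are 65+: 128 to 149 cases there, and 43 to 32 in each younger band.
- Equal thirds, for comparison: 71 cases and 171 controls.

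**4. Power (unadjusted, two-sided 5%).** With p0 the control exposure and an odds ratio of 2, p1 = 2·p0/(1 + p0), which is 0.621 at 45% and 0.276 at 16%. Power = Φ[(d − 1.96·SE0)/SE1], where d = p1 − p0, SE0 = √{p̄(1 − p̄)(1/n1 + 1/n0)} and SE1 = √{p1(1 − p1)/n1 + p0(1 − p0)/n0}.

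Example, 37/156 at 45%: d = 0.171, p̄ = 0.483, SE0 = 0.0914, SE1 = 0.0892, so power = Φ(−0.09) = 46%.

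| Model (cases/controls) | Power, 45% exposed | Power, 16% exposed |
|---|---|---|
| Pooled, 213/512 | 99% | 94% |
| 65+, 138/200 | about 87% | 73% |
| Each younger band, 37/156 | 46% | 39% |
| Equal thirds, 71/171 | 68% | 54% |

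Holding controls at 200 and 156, the 60% to 70% range gives 86% to 89% in 65+ and 51% to 42% in each younger band at 45% exposure.

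**5. Interval width.** The standard error of the log odds ratio is √{1/(n1·p1(1 − p1)) + 1/(n0·p0(1 − p0))}. Relative to the pooled model it is 1.35 (45% exposed) to 1.39 (16%) times larger in 65+, and 2.25 to 2.19 times larger in a younger band: about 1.4 and 2.2.

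**6. Candidates against cases.** Appendix 1 item 5.7 alone has about 31 comorbidity rows. Cases per row: 213/31 = 6.9 pooled, 138/31 = 4.5 in 65+, 37/31 = 1.2 in a younger band.

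**The case against.** Stratifying by age is legitimate where effects are expected to differ with age, and pooling has its own cost. One can also read the opening of 7.3 as an all-ages model to which the age-band models are added, and can point to age being marked for multivariate use in Appendix 1. But the text says the regression is performed separately by age group and names nothing else, and continuous age inside a band gives only a within-band slope.

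Four stronger readings are tempting, and the documents do not support them:

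- **That age over 65 cannot be estimated at all.** The power statement is unadjusted, and the unrestricted univariate analysis in 7.2 can deliver that crude comparison with every case and control. Only the adjusted contrast is lost.
- **That each model has about 71 cases.** That is 213/3. The SAP's own 65% puts nearly twice as many in 65+ and about half as many in each younger band, so the loss is moderate in one model and severe in two.
- **That age groups cannot be compared across separate models.** The bands are disjoint, so log odds ratios from models with the same covariates can be tested for heterogeneity. The accurate point is that no such test is planned and that separate selection may leave different covariates in each band.
- **That every diagnostic class will be modelled within every age band.** Objective 2 in SAP 2.5 asks for risk factors by class, but 7.3 names only case/control as the dependent variable.

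**Conclusion.** The concern holds in this limited form. As written, 7.3 yields no adjusted 65+ versus younger odds ratio. That follows from the text and needs no assumption.

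The loss of precision is real and uneven. Its size rests on the earlier study's age proportions, no patients under 18 and an equal split of younger patients, and the documents confirm none of these. Any cases under 18 would lower the counts in the three planned models. The power figures are unadjusted and serve to compare the designs, not to forecast the power of the fitted models. Under either the SAP's proportions or equal thirds, at least two of the three models have well under 80% power for an odds ratio of 2, where the pooled data have over 90%.

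**What to change.** In SAP 7.3, make the main regression one model across all ages, with age as a covariate (a spline or bands) and a small number of pre-stated age-by-exposure interactions for key exposures. Report age-specific odds ratios from that model. Keep the separate age-band models as a descriptive supplement and say so in the text.

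The cost is SAP wording, since age and all exposures are already collected. The downside is that confounder effects are assumed common across ages unless an interaction is fitted, and the SAP should state this.
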